5.3.3 Radiographic Assessments

Quantitative and qualitative radiographic assessment of the pre-operative AP, lateral, and left and right lateral bending images, as well as post-operative AP and lateral images will be performed. **Please note:** All images must be from head to hip to ensure that all relevant landmarks and instrumentation are captured and all measurements can be completed.

Radiographic assessments being performed include:

- Quantitative assessment:
 - Identification of apex level
 - Pre-operative assessment of curve flexibility will be performed by comparing the Cobb angles on the left and right lateral bending radiographs with the pre-operative standing AP and Lateral radiographs and recording percentage change in the Cobb angle
 - Assessment of coronal and sagittal curve correction will be performed by comparing the Cobb angles on the pre-operative AP and lateral radiographs with the standing AP and Lateral radiographs at each post-operative visit and recording percentage change in the Cobb angle
 - Pre-operative Risser Score
 - Global sagittal balance as measured by the distance from the C7 plumb line to the perpendicular line drawn from the superior posterior endplate of the S1 vertebral body (Central Sacral Vertical Line (CSV))
 - If the C7 plumb line falls behind the CSV, global sagittal balance is negative
 - Pelvic incidence, as defined by pelvic tilt + sacral slope
- Qualitative assessment
 - Pre-operative Lenke type classification
 - Lumbar spine modifier (A, B, or C) and/ thoracic sagittal profiles (hypo, normal, hyper)
 - Device condition post-operatively

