12.2 Study Hypothesis

The primary objective of this study is to evaluate the effectiveness of the MESA Rail Deformity System in terms of restoring and maintaining thoracic kyphosis in the treatment of patients with symptomatic AIS. The primary effectiveness endpoint is the rate of overall subject success (minimal loss of thoracic kyphosis) at 24 months. The primary hypothesis of this trial is that the clinical performance of the K2M MESA Rail implant is non-inferior to the clinical performance achieved and achieved with fusion utilizing a standard Ø5.5mm or Ø4.5mm CoCr rod.

A PubMed literature review was conducted to assemble relevant publications utilizing results from posterior instrumentation fusion surgeries in patients with AIS. Searches included all peer-reviewed journals published between January 2000 and March 2013. Sample sizes, patient populations, evaluated variables, results, and recorded complications were assessed for each selected article. Only data regarding thoracic kyphosis measurements of single-stage posterior fusion cases were incorporated into the thoracic kyphosis table used for statistical analysis. Articles were entirely excluded from the statistical analysis if results combined data from multi-stage cases or if data were extracted through meta-analysis.

The following table gives the preoperative thoracic kyphosis measurements as well as the thoracic kyphosis measurements collected at the last follow-up period from all relevant posterior fusion surgeries in patients with AIS:

| Thoracic Kyphosis | | | | | | | | | |
|----------------------------------|-----|-------|------|---------|------|------|------|---------------------|-------------|
| paper # | n | Preop | | Last FU | | Diff | | Mean difference x N | Std Dev x N |
| | | Mean | SD | Mean | SD | Mean | SD | | |
| 1 ¹ | 9 | 31.9 | 10.4 | 26.0 | 9.8 | 5.9 | 10.1 | 53.1 | 90.9 |
| 1 | 3 | 31.0 | 9.5 | 29.7 | 5.5 | 1.3 | 7.5 | 3.9 | 22.5 |
| 1 | 34 | 28.2 | 13.0 | 26.5 | 11.0 | 1.7 | 12.0 | 57.8 | 408.0 |
| 1 | 9 | 23.0 | 8.0 | 23.0 | 11.0 | 0.0 | 9.5 | 0.0 | 85.5 |
| 1 | 60 | 26.7 | 13.0 | 25.0 | 9.6 | 1.7 | 11.3 | 102.0 | 678.0 |
| 1 | 31 | 22.8 | 11.0 | 25.7 | 8.8 | -2.9 | 9.9 | -89.9 | 306.9 |
| 2 ² | 83 | 23.0 | 12.0 | 20.2 | 8.4 | 2.8 | 11.4 | 234.9 | 946.2 |
| 3 ³ | 111 | 29.0 | 14.0 | 23.0 | 10.8 | 6.0 | 12.2 | 666.0 | 1354.2 |
| 3 | 299 | 22.0 | 14.1 | 22.0 | 10.3 | 1.0 | 5.0 | 299.0 | 1495.0 |
| Weighted Mean Difference and SD: | | | | | | | | 2.1 | 8.4 |

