The study hypothesis is that the RAIL system is superior to other systems in Thoracic Kyphosis Correction. The hypotheses can be written:

$$\begin{aligned} H_0: \mu_R &< OPC - \delta \\ H_1: \mu_R &\geq OPC - \delta \end{aligned}$$

where μ_R is the mean Thoracic Kyphosis Correction of the RAIL system and OPC is the Objective Performance Criteria of 2.2 and $\delta = 2$ degrees.

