12.3 Sample Size

If the mean Thoracic Kyphosis Correction of the RAIL system is 4.0 with a standard deviation of 8.4, then 173 subjects provides 80% power to detect a statistically significant difference between the mean correction and the OPC of 2.2 using a two-sided one-sample t-test at a significance level of 0.05. In order to account for approximately 15% attrition, based on clinical experience, 204 subjects will be enrolled.

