12.5 Analysis of Primary Endpoint

The primary effectiveness endpoint will be evaluated by a two-sided exact test of the MESA Rail implant success rate (mean thoracic correction) against the literature reported mean thoracic correction of 2.2 degrees.

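### The primary kyphosis endpoint has no stated sign: the 2.2-degree benchmark matches a table of kyphosis loss, while H1 and the planning mean treat larger values as better

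*Combined protocol and SAP*

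**What the plan says.** Section 12.2 of the combined protocol and SAP gives the aim as "restoring and maintaining thoracic kyphosis in the treatment of patients with symptomatic AIS". It then states: "The primary effectiveness endpoint is the rate of overall subject success (minimal loss of thoracic kyphosis) at 24 months". Both describe less loss as better.

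The same section tabulates pre-operative and last follow-up kyphosis from the literature, with a difference column and a pooled mean difference of 2.1 (SD 8.4). One row, in which kyphosis rises from 22.8 to 25.7, reads "1 | 31 | 22.8 | 11.0 | 25.7 | 8.8 | -2.9 | 9.9 | -89.9 | 306.9", so a rise is scored as negative.

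Section 12.2 next claims superiority in kyphosis correction and writes H0: μ_R < OPC − δ against H1: μ_R ≥ OPC − δ, where μ_R is the "mean Thoracic Kyphosis Correction of the RAIL system and OPC is the Objective Performance Criteria of 2.2" and δ is 2 degrees. Section 12.3 begins its power statement with "If the mean Thoracic Kyphosis Correction of the RAIL system is 4.0 with a standard deviation of 8.4" and compares that mean with 2.2. Section 12.5 tests the device "against the literature reported mean thoracic correction of 2.2 degrees".

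The only other account of how correction is derived is in Section 5.3.3: "Assessment of coronal and sagittal curve correction will be performed by comparing the Cobb angles on the pre-operative AP and lateral radiographs" with those at each post-operative visit. The result is recorded as a percentage change, without a sign convention and not in degrees.

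**The concern.** The benchmark and the decision direction appear to sit on opposite scales. If correction is scored as in the literature table (pre-operative minus follow-up), 2.2 is a sensible benchmark, but H1 and the planning mean of 4.0 point toward more loss of kyphosis. If correction means a gain (follow-up minus pre-operative), H1 points the intended way, but the literature value belongs at about −2.1 and not at +2.2.

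This is a single-arm study and the benchmark is its only comparator in the primary analysis. If the sign is chosen after the data are seen, that choice decides whether the same result counts as success or failure.

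**Working it through.** **1. The plan's own sample size.** Inputs from 12.3: mean 4.0, benchmark 2.2, SD 8.4, two-sided 0.05, one-sample t-test. The difference is 4.0 − 2.2 = 1.8. The noncentral t gives 80.0% power at n = 173, and 173/(1 − 0.15) rounds up to 204. Both figures reproduce. They depend only on |4.0 − 2.2|, so they say nothing about direction.

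**2. The sign of the table.** Pre-operative minus last follow-up equals the printed difference in eight of nine rows. Examples: 29.0 − 23.0 = +6.0; 22.8 − 25.7 = −2.9. The exception is "3 | 299 | 22.0 | 14.1 | 22.0 | 10.3 | 1.0 | 5.0 | 299.0 | 1495.0", where 22.0 − 22.0 = 0 but 1.0 is printed. Positive therefore means loss.

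**3. The pooled value** (total n = 639):
- from the printed products: 1326.8/639 = 2.08, printed as 2.1;
- from the printed pre-operative and follow-up means: 1025.3/639 = 1.60.

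Both are mean losses. Neither gives 2.2.

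**4. The benchmark error on a gain scale.** The literature value becomes −2.1, so the gap to +2.2 is 4.3 degrees. It is 4.4 if −2.2 is used, and 3.8 if −1.6 is used. The powered difference is 1.8.

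**5. What the test would show.** The noncentrality is (μ − benchmark)·√n/8.4, with two-sided 0.05 and n = 173 unless stated.

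| True mean | Scale | Compared with | Result | Probability |
|---|---|---|---|---|
| 0 (kyphosis unchanged on average) | either | 2.2 | significantly below | 0.929 (0.961 at n = 204) |
| 4.0 (loss) | table's | 2.2 | significantly above | 0.800 |
| −2.1 (equal to the literature) | gain | 2.2 | significantly below | >0.999 |
| 4.0 (loss) | table's | 0.2 | significantly above | >0.999 |
| 0 | either | 0.2 | significantly above | 0.012 |

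The 0.2 in the last two rows is OPC − δ = 2.2 − 2. The plan gives no alpha or sidedness for that threshold; two-sided 0.05 is assumed.

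**6. Evaluable subjects for 80% power, by difference** (SD 8.4, two-sided 0.05): 1.6 needs 219; 1.8 needs 173; 2.0 needs 141; 2.1 needs 128; 2.2 needs 117.

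**The case against.** Several points can be made for the plan.

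- **The source of 2.2 is not stated outright.** The table prints 2.1 and no recomputation gives 2.2. That is true, and the link is an inference. It is a strong one: 12.5 attributes 2.2 to the literature, this is the only literature table given, and its SD of 8.4 is the planning SD.
- **Correction could mean reducing kyphosis.** The table, H1, the planning mean and 12.5 would then agree in sign. But the numerical plan would contradict minimal loss in 12.2 and the restoration and maintenance objective in 5.1. The conflict moves; it does not go away.
- **Minimal loss describes a success rate, whereas the hypotheses concern a mean.** That is a separate inconsistency. It does not supply a sign.
- **The two-sided test is neutral.** Sections 12.3 and 12.5 taken alone name no winning direction, so the probabilities against 2.2 are not failure rates under a stated decision rule. This stands as a caution on wording. The direction comes from H1 and the superiority claim in 12.2.
- **The 1.6 figures are conditional.** The n = 299 row may carry a difference and SD taken directly from the cited paper: its 5.0 is not the average of 14.1 and 10.3, which is 12.2, whereas the paper 1 rows do use that average. The row needs checking, and 1.6 is only a sensitivity value.

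**Conclusion.** The concern holds. The stated objective, the literature benchmark and the hypotheses cannot all stand on one scale, and no section says which should give way. On the table's scale, the favourable side of H1 is greater kyphosis loss. On a gain scale, the benchmark is about 4.3 degrees stricter than the literature it is meant to represent, more than twice the powered difference. On either scale, a device that leaves mean kyphosis unchanged would most likely be found significantly below 2.2.

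These sizes rest on the plan's SD of 8.4, on 173 evaluable subjects (204 where stated) and on 2.2 deriving from the table. The primary conclusion can be reversed by the sign chosen, so this must be settled before outcome data are analysed.

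**What to change.** Define one signed change score in degrees for T4–T12 kyphosis, and name its baseline. The table and Section 5.3.3 both use the pre-operative film; if maintenance from the initial post-operative film is meant, say so. State which direction is success, and whether this applies to every thoracic sagittal profile, since Section 4.2 does not restrict them.

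Then put the benchmark, hypotheses and planning mean on that scale in 12.2, 12.3 and 12.5. For example, with loss = pre-operative minus 24-month kyphosis:
- superiority: H1: μ_R < benchmark;
- non-inferiority: H1: μ_R < benchmark + δ.

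State alpha and sidedness for whichever is primary. Reconcile 2.2 with the table's 2.1, and check the n = 299 row against its source.

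These are text changes with no new data collection, but the sample size must be re-justified. On the loss scale, 173 keeps 80% power for superiority only if the assumed mean loss is 1.8 degrees below the benchmark: 0.4 against 2.2, or 0.3 against 2.1. If zero mean loss is assumed, 117 evaluable subjects are needed for a benchmark of 2.2, 128 for 2.1 and 219 for 1.6. Non-inferiority with δ = 2 and a true loss equal to the benchmark needs 141, assuming one-sided 0.025. So 173 may be ample or too few. If it is kept, restate the power at that number.

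### The OPC of 2.2 degrees used in 12.2, 12.3 and 12.5 does not match its only source table, which prints 2.1 and computes to 2.08, and the difference is not explained

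*Combined protocol and SAP*

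**What the plan says.** The value 2.2 appears three times.

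- Section 12.2 defines it: "OPC is the Objective Performance Criteria of 2.2".
- Section 12.3 sizes the trial on the difference "between the mean correction and the OPC of 2.2 using a two-sided one-sample t-test", assuming a MESA Rail mean of 4.0 and an SD of 8.4. It arrives at 173 evaluable subjects for 80% power, and 204 enrolled after about 15% attrition.
- Section 12.5 tests the primary endpoint "against the literature reported mean thoracic correction of 2.2 degrees".

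The only literature summary is the thoracic kyphosis table in Section 12.2: nine rows from three papers, 639 patients. Its last line reads "Weighted Mean Difference and SD: | | | | | | | | 2.1 | 8.4". The largest row reads "3 | 299 | 22.0 | 14.1 | 22.0 | 10.3 | 1.0 | 5.0 | 299.0 | 1495.0". The selection rule given for the table is: "Only data regarding thoracic kyphosis measurements of single-stage posterior fusion cases were incorporated into the thoracic kyphosis table used for statistical analysis".

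The Synopsis and Section 4.3 define the control as 5.5 mm or 4.5 mm CoCr pedicle-screw and rod systems.

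**The concern.** In a single-arm study the benchmark is the whole control. Section 12.5 presents 2.2 as a number read from the literature, but the table meant to supply it shows 2.1. A reader cannot tell whether 2.2 is a slip, a value from another version of the table, or a deliberate choice. The number matters because it is the value the mean is compared with in the sample size and in the primary analysis.

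Two features of the table add to the traceability problem. The row with the most weight is not consistent on its face. And the stated selection rule does not mention the features that define the control group.

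**Working it through.** **1. The plan's own sample size.** Inputs from Section 12.3: mean 4.0, OPC 2.2, SD 8.4, two-sided alpha 0.05, power 80%. For a one-sample t-test the effect is 4.0 − 2.2 = 1.8 and the noncentrality is (1.8/8.4)·√n. The noncentral t distribution gives power 79.8% at n=172 and 80.0% at n=173. Then 173/0.85 = 203.5, rounded up to 204. Both figures reproduce, so 2.2 really was used in the sizing.

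**2. The table mean.** Formula: sum of (mean difference × n) / sum of n, using the printed products.

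| Row | n | Mean difference × n |
|---|---|---|
| Paper 1 | 9 | 53.1 |
| Paper 1 | 3 | 3.9 |
| Paper 1 | 34 | 57.8 |
| Paper 1 | 9 | 0.0 |
| Paper 1 | 60 | 102.0 |
| Paper 1 | 31 | −89.9 |
| Paper 2 | 83 | 234.9 |
| Paper 3 | 111 | 666.0 |
| Paper 3 | 299 | 299.0 |
| Total | 639 | 1326.8 |

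1326.8/639 = 2.076, which rounds to the printed 2.1.

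**3. Other ways of forming the mean.**

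- Paper 2 product recomputed as 83 × 2.8 = 232.4: 1324.3/639 = 2.07.
- Preop minus last follow-up means in every row: 1025.3/639 = 1.60.
- Unweighted mean of the nine differences: 1.94.
- Inverse-variance weighted mean: 1.31.
- Leaving out one row at a time: 1.25 to 3.02, with none rounding to 2.2.

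No variant tried gives 2.2.

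**4. Size of the discrepancy.** Same t-test, mean 4.0, SD 8.4.

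| OPC | Effect | n for 80% power | Power at n=173 |
|---|---|---|---|
| 2.2 | 1.8 | 173 | 80.0% |
| 2.1 | 1.9 | 156 | 84.1% |

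The half-width at n=173 is 1.974 × 8.4/√173 = 1.26. The observed mean needed for significance is therefore 2.2 + 1.26 = 3.46, or 2.1 + 1.26 = 3.36.

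**5. The n=299 row.** It carries 299/639 = 47% of the weight. Its preop and follow-up means are both 22.0, but its difference is printed as 1.0. Its difference SD is 5.0, while its two SDs are 14.1 and 10.3, averaging 12.2. In all six paper 1 rows the difference SD equals the average of the two SDs, for example (10.4 + 9.8)/2 = 10.1. So this row was filled in by a different route.

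**6. The SD of 8.4.** The table averages SDs by n: 5387.2/639 = 8.43. Without the n=299 row the average is 3892.2/340 = 11.45, so that row drives the result. Pooling the same nine SDs as variances, √[Σ(n−1)SD²/(639−9)] = √(51355.7/630) = 9.03. With SD 9.03, 173 subjects give 78.6% power at OPC 2.1 (180 needed for 80%) and 74.1% at OPC 2.2.

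**7. Selection rule against control definition.** The Synopsis and Section 4.3 specify rod material (CoCr), diameter (5.5 or 4.5 mm) and anchor type (pedicle screw). The rule stated in Section 12.2 specifies single-stage posterior fusion, and the table has no column for any of the three features. The reference list gives paper 3, which supplies 111 + 299 = 410 of the 639 patients (64%), a title naming three types of instrumentation.

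**The case against.** An OPC is a chosen benchmark and may be set above a pooled mean. The gap is 0.1 degree, and on the plan's reading 2.2 is the harder value to beat, so the discrepancy gives the device no advantage. This stands as to size and direction. It does not rescue Section 12.5, which describes 2.2 as the literature mean and not as a chosen margin above it. Damage to the table in text extraction is an unlikely explanation, since the printed products agree with the printed 2.1.

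On the n=299 row, equal printed means with a difference of 1.0 could reflect a change reported directly by the paper, with its own SD. A reader might infer that the row is wrong; the documents do not establish that.

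On the comparator, a reader might infer that the table is not a CoCr series. The documents do not support that either. Section 12.2 speaks of relevant publications and says patient populations were assessed for each selected article, without printing the relevance criteria. Section 12.1 says the comparison is with CoCr outcomes. A title naming three instrumentation types does not settle rod material or anchor type. What stands is that the match has not been shown.

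**Conclusion.** The mismatch is established: 2.2 in three sections against 2.1 printed and 2.08 computed in the only source, with no explanation. It is a traceability defect in the benchmark of the primary analysis. It is tempting to conclude that the trial is mis-sized because of it, but the documents do not support that. With the plan's mean of 4.0 and SD of 8.4, moving to 2.1 lowers the requirement from 173 to 156.

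The power figures rest on the two-sided t-test of Section 12.3. They do not carry over to the exact test of a success rate named in Section 12.5. They also depend on the averaged SD: at about 9.03, 173 evaluable subjects fall slightly short of 80% power at 2.1 and further short at 2.2.

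The n=299 row is a query. The link between the table and the Section 4.3 control is not shown, which is weaker than saying it is wrong. The sign convention of the table's difference column and the boundary implied by OPC − δ in Section 12.2 are separate matters and add no weight here.

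**What to change.** 1. Check the n=299 row against its source paper, both the difference of 1.0 and the SD of 5.0, and note whether they are directly reported change values.
2. Set one OPC equal to the resulting table value (2.1 if the table stands), use it in Sections 12.2, 12.3 and 12.5, and restate the power. If 2.2 is kept, give the reason and stop calling it the literature mean in Section 12.5.
3. In restating power, say that 8.4 is an n-weighted average of SDs, and give the result for the variance-pooled SD alongside it.
4. Record rod material, diameter and anchor type for each table row from the three cited papers. If only some rows meet Section 4.3, restrict the table to them and recompute the mean and SD. If the rows do not qualify, describe the benchmark as published posterior instrumentation series in AIS.

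The cost is reading three papers, one recalculation and some wording; no new trial data are needed. With OPC 2.1 and SD 8.4 no subjects are added. With SD 9.03 the requirement is 180 evaluable, and 180/0.85 = 211.8, so 212 enrolled against the planned 204. The other costs are that 2.1 is slightly easier to beat than 2.2, and that a restricted table could move both the OPC and the SD.

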5 STUDY OBJECTIVES/OUTCOMES

5.1 Primary Effectiveness Objective

The primary effectiveness objective is:

Restoration and maintenance of thoracic kyphosis and coronal curve correction.

- Quantitative assessment:
 - Cobb Angles – Coronal and Sagittal
 - Thoracic kyphosis as measured from the upper endplate of T4 to the lower endplate of T12
 - Lumbar lordosis as measured from the lower endplate of L1 to the upper endplate of S1

The increased stiffness of the MESA Rail is designed for the restoration and maintenance of thoracic kyphosis as well as coronal correction of deformities such as AIS after surgery. The restoration and subsequent maintenance of the thoracic kyphosis and coronal curve correction during surgery is expected to be as good as if not better than results reported for standard Ø5.5mm and Ø4.5mm CoCr pedicle screw and rod systems in these patient populations.

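### The formal hypotheses in 12.2 set a bar of 0.2 degrees through an unjustified 2-degree margin, which matches neither the superiority claim they express nor the sizing and primary test, both against 2.2

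*Combined protocol and SAP*

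**What the plan says.** Section 12.2 of the combined protocol and SAP describes the aim in two ways. It first gives as the primary hypothesis that "the clinical performance of the K2M MESA Rail implant is non-inferior to the clinical performance" of CoCr rods. After the literature table it says: "The study hypothesis is that the RAIL system is superior to other systems in Thoracic Kyphosis Correction". The formula that follows has H0: mean < OPC - delta and H1: mean >= OPC - delta, where "OPC is the Objective Performance Criteria of 2.2" and delta is 2 degrees. I found no justification for delta in the document.

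The other sections do not use delta:

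- Section 12.3 sizes the trial so that "173 subjects provides 80% power to detect a statistically significant difference between the mean correction and the OPC of 2.2", with a two-sided one-sample t-test at 0.05.
- Section 12.5 plans a two-sided test against the literature mean of 2.2 degrees.
- Section 6 gives the endpoint as showing that the result is better than with similar CoCr systems.
- Section 5.1 expects that restoration and maintenance "is expected to be as good as if not better than results reported for standard" CoCr systems.

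**The concern.** The formula is the only formal statement of the hypotheses, and it is not the hypothesis that the rest of the plan sizes and tests. Rejecting its H0 shows that the mean exceeds 0.2 degrees. That supports neither the superiority sentence directly above it nor the endpoint in section 6.

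The margin is also hard to square with the plan's own figures. A gain of 1.8 degrees over the benchmark is what the trial is built to detect, yet a shortfall of up to 2.0 degrees would satisfy H1. With no rationale given, a reader cannot tell whether 2 degrees was meant as a clinically tolerable loss.

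At stake is which statement governs the conclusion. If the primary test against 2.2 fails, 12.2 leaves a much easier written criterion to turn to, and it could be read as evidence of performance as good as CoCr.

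**Working it through.** **Inputs.** OPC 2.2 and delta 2 (12.2). Assumed Rail mean 4.0, SD 8.4, 173 evaluable and 204 enrolled, two-sided alpha 0.05 (12.3). The documents give no level for a non-inferiority test. I assume one-sided 0.025, half of the stated two-sided 0.05, and show one-sided 0.05 as well.

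**1. The plan's own figure.** Difference to detect: 4.0 - 2.2 = 1.8. With SD 8.4, two-sided 0.05 and the noncentral t distribution, n = 173 gives power 80.03%. Attrition: 173/0.85 = 203.5, so 204. Both figures reproduce, and they reproduce for a test against 2.2 with no margin.

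**2. The bar in 12.2.** OPC - delta = 2.2 - 2 = 0.2 degrees. Margin over benchmark: 2/2.2 = 91%. Margin over sized-for difference: 2/1.8 = 1.11.

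**3. The 12.2 formula as a decision rule, larger taken as better.** The rule passes if the observed mean exceeds 0.2 + t × SE, with SE = 8.4/√n.

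- n = 173: SE = 0.639, t = 1.974, limit 0.2 + 1.26 = 1.46 (66% of the OPC).
- n = 204: SE = 0.588, t = 1.972, limit 0.2 + 1.16 = 1.36 (62% of the OPC).

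For comparison, the test in 12.3 and 12.5 at n = 173 needs an observed mean above 2.2 + 1.26 = 3.46 for a significant advantage.

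Probability of passing the 12.2 rule (noncentral t, SD 8.4):

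| True mean | n = 173, 0.025 | n = 204, 0.025 | n = 173, 0.05 | n = 204, 0.05 |
|---|---|---|---|---|
| 1.1 (half the OPC) | 29% | 33% | 40% | 45% |
| 2.2 (equal to the OPC) | 88% | 92% | 93% | 96% |

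An *observed* mean of 1.1 does not pass. At one-sided 0.025, t = 0.9/0.639 = 1.41 and p = 0.080 with 173 subjects, and p = 0.064 with 204. At one-sided 0.05 the limits are 1.26 and 1.17, so 1.1 still fails.

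**4. Direction of the scale.** The difference column of the 12.2 literature table is pre-operative minus last follow-up: 31.9 - 26.0 = 5.9 and 22.8 - 25.7 = -2.9. (The last row is an exception: it prints 1.0 where both means are 22.0.) A positive value is therefore a loss of kyphosis, and the same section describes success as minimal loss. The hypotheses, 12.3 and 12.5 call the quantity a correction. On the table's scale, a mean of 1.1 is half the benchmark loss, the planning value of 4.0 is a greater loss than the benchmark, and H1 points the wrong way. Step 3 holds only on the correction reading.

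**The case against.** The strongest objection is that delta drives no planned test. It appears only in the 12.2 hypotheses, while the sizing and the primary analysis are against 2.2. If those govern, the margin has no effect on the result. This stands, and it limits the point to a mismatch that must be removed. It does not make the formula harmless, because 12.2 also names non-inferiority as the primary hypothesis and delta is the only written route to that claim.

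A reader might infer that a Rail with half the benchmark correction will be declared non-inferior. The documents do not support this. An observed mean of 1.1 fails at both sample sizes, and a true mean of 1.1 fails about 71% of the time at n = 173 (one-sided 0.025). On the table's scale, half the benchmark would be the better result. A reader might also infer that the trial would report equality with CoCr on the strength of the 0.2 bar, but no section describes such a report.

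The ratio arguments have limits too. The benchmark is a before-after change near zero, with table rows of 0.0 and -2.9, so many margins in degrees would look large as a share of it. A non-inferiority margin need not be smaller than the gain assumed for superiority sizing, since the two answer different questions. What remains is that the plan gives no reason why 2 degrees is tolerable.

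**Conclusion.** The point holds as an inconsistency in the formal hypotheses. As written, H1 sets a threshold of 0.2 degrees, which fits neither the superiority claim it is meant to express nor the sizing and primary test. The margin is unexplained, equals 91% of the OPC, and exceeds the 1.8-degree sized-for difference.

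If the formula were used as the decision rule, observed means from about 1.36 to 1.46 upward would pass, and a true mean of 1.1 would pass 29% to 33% of the time (40% to 45% at one-sided 0.05). These figures rest on SD 8.4, 173 to 204 analysed subjects, an assumed one-sided level, and larger being better, which the literature table contradicts. They do not show that the planned primary test is lenient: that test is against 2.2.

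**What to change.** 1. Settle the sign of the endpoint, and use one definition in the 12.2 table, the hypotheses, 12.3 and 12.5.
2. Delete delta from 12.2 and restate H0 and H1 against the OPC, to match 12.3 and 12.5.
3. Remove the non-inferiority statement from 12.2.
4. Report the mean with its two-sided 95% confidence interval beside the OPC.
5. State that a non-significant result against the OPC does not show performance as good as CoCr.

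This changes wording only and needs no more patients. The plan gives up a non-inferiority claim that it neither sized nor planned to test.

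If the sponsor wants to keep non-inferiority, a margin must be justified on the settled scale before data are seen, and the sample size checked against it. I propose no value, because the documents give no basis for one and the choice is costly. For illustration, on the correction reading, a margin of half the OPC (1.1) would have 40% power at a true mean of 2.2 with 173 subjects. Restoring 80% would take 460 evaluable subjects, or 460/0.85 = 541.2, so 542 enrolled.
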